Meta-analyses have demonstrated the efficacy of ACT compared to placebo, however, the way in which ACT is effective is less understood (Öst, 2014). Therefore, it is not only crucial to provide further evidence of whether ACT is an effective intervention for older adults, it is important to understand the processes that make it effective. Randomised controlled trials (RCTs) are often used as the 'gold standard' in establishing the efficacy of a psychotherapeutic model (Hariton & Locascio, 2018). However, in order to demonstrate causality, RCTs require the application of strict criteria to the study variables (e.g. participant diagnoses, age range) or the removal of extraneous factors (e.g. preventing participants changing medications during the study). This has led to criticisms as to whether RCTs are wholly appropriate when investigating the complexities of how and why a psychotherapy is or is not effective (Elliott, 2002).

An ideal methodology to investigate such issues is the Hermeneutic Single Case Efficacy Design (HSCED; Elliott, 2002), which is a critical and interpretive approach to assess the intervention effects for single therapy cases in a naturalistic clinical setting. There are longstanding arguments whether psychotherapy operates through modality specific factors (ACT in this study), or through non-specific factors common to all psychotherapies (e.g. the therapeutic alliance or a client's expectations of treatment; Mulder, Murray & Rucklidge, 2017). It is also important to recognise the impact that events outside of the therapy session, extra-therapeutic factors, have on change within the client (e.g. a significant loss, change in medications). The HSCED acknowledges that there are numerous factors which contribute towards change (modality-specific, non-specific and extra-therapeutic), and it actively seeks to measure and analyse these. The utilisation of a case series (rather than individual case

study) allows for a cross-synthesis of what does and does not contribute towards change between-participants.

This study provides an original contribution towards the field as it applies a therapeutic intervention (ACT) that is under researched within the older adult population. Furthermore, it utilises a methodology that is not only ideal in addressing the complex processes of efficacy, but which has also never been used to investigate ACT with older adults experiencing psychological distress.

STUDY OBJECTIVES AND PURPOSE

PURPOSE

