The purpose of the study is to examine whether ACT can be an effective intervention in increasing quality of life in older adults (aged 65+), presenting to older adult mental health service with psychological difficulties, as well as why ACT is effective.

PRIMARY OBJECTIVE

In this study we aim to investigate the efficacy of ACT for supporting older adult clients experiencing psychological distress.

SECONDARY OBJECTIVE(S)

In addressing the primary objective, we will be guided by three fundamental questions: (1) Do (meaningful) changes occur for client-participants over the course of ACT intervention? (2) Are observed changes broadly attributable to the ACT intervention? (3) What specific factors (ACT-specific, non-specific, extra-therapeutic) contribute to observed changes?

The study will also identify adaptations that may be facilitative of change when using ACT with older adult clients, **with consideration of the impact that moving the study to a telephone/videocall delivered intervention.**

OUTCOME MEASURES

PRIMARY OUTCOME MEASURE

1. Change in quality of life assessed using the Older People's Quality of Life questionnaire (OPQOL-brief; Bowling, Hankins, Windle, Bilotta, & Grant, 2013). Completed by participant.

SECONDARY OUTCOMES

Symptom measures

1. Client's level of cognitive functioning assessed using the Montreal Cognitive Assessment (MoCA; Nasreddine et al., 2005). Completed by MHSOP team with the participant.
2. Changes in symptoms of anxiety and depression assessed with the Hospital Anxiety and Depression Scale (HADS; Zigmond & Snaith, 1983). Completed by the participant.

Change measures

1. Change in/progress on client's goals assessed using the Simplified Personal Questionnaire (PQ; Elliot, Mack, & Shapiro, 1999). Completed by participant with guidance from therapist.
2. Client's attribution of change and view on therapy assessed with the Change Interview (Elliott, Slatick, & Urman, 2001). Conducted by secondary researcher with participant.

Process measures

1. Change in psychological flexibility assessed using the CompACT-8 (Morris, Dawson, & Golijani-Moghaddam, 2019). Completed by participant.

Session measures

1. Change in client's weekly level of quality of life assessed using the Outcome Rating Scale (ORS; Miller, Duncan, Brown, Sparks & Claud, 2003). Completed by participant.
2. Change in therapeutic alliance assessed with the Session Rating Scale (SRS; Duncan et al., 2003). Completed by participant.

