Exploratory/Tertiary Objectives	
 1. Beneficial adaptations for ACT. 2. Impact of telephone/videocall and adaptations to this. 	
 1. Noted throughout the study by researcher and commented on in final write up. 2. Noted throughout the study by researcher, factored into impact of results, and commented on in final write up.

STUDY DESIGN

To address the aims and sub-objectives listed previously, the study will employ an adjudicated Hermeneutic Single Case Efficacy Design (HSCED) series. Following Elliott's

(2002; Elliott et al., 2009) approach, the first step for a HSCED is the formation of rich case records. Developed for each client, these consist of data from various time points in the study, and include demographic, quantitative (outcome measures, treatment fidelity measures etc.) and qualitative sources (Change Interview, therapy feedback, therapy process notes and recordings). The rich case records are then cross-referenced and synthesised into an affirmative and sceptic brief. These briefs are then presented to an expert panel to be adjudicated on the process of change (see Figure 1).

[figure not shown]

Figure 1: the HSCED process (Stephen et al., 2011).

Affirmative brief

The purpose of the affirmative brief is to demonstrate direct links between the therapeutic intervention and outcomes, and is divided into three parts: 1) a brief of the main lines of argument for these links; 2) a rebuttal against the arguments made in the sceptic brief; and 3) a concluding summary narrative (Stephen et al., 2011). The affirmative brief draws evidence from five areas (see Table 1), with evidence in at least two areas required to warrant adjudication (Elliott, 2002).

Sceptic brief

The opposing sceptic brief demonstrates possible nontherapy processes which could account for change (Table 2), and uses the same structure of a brief, a rebuttal, and a narrative summary. Elliott (2002) talks about the sceptic brief being developed in a manner of good-faith to determine what non-therapy effects may have led to change.

DATA ANALYSIS

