To facilitate the cross-referencing of rich case records, several methods of analysis will be employed, dependent on the evidence area required for the affirmative or sceptic brief. These are outlined in Tables 1 and 2, respectively. All analyses will be completed using SPSS (Version 25.0; IBM Corp, 2017) or Microsoft Excel (Version 15.0.5179.1000; Microsoft Corporation, 2013). Analyses will be performed by the student researcher/therapist either at the MHSOP or the Universities of Lincoln or Nottingham. No data containing confidential information will be analysed outside of the MHSOP, in line with relevant NHS Trust policies.

Table 1		
Direct evidence for links between therapy process and outcome, from Elliott (2002).		
Direct evidence area	Description	Method of evaluation (specific analysis method)
1. Retrospective attribution	Change attributed by client to the therapy	Content of Change Interview (Framework Analysis)
2. Process-outcome mapping	Content of post-therapy changes correspond to specific processes within therapy	Correlations between within therapy measures (HAT), and quantitative outcome measures (Pearson correlation, or Spearman correlation if assumptions of normal distribution not met).
3. Within-therapy process-outcome correlation	In-therapy process variables covary with week-to-week changes in client problems	Correlations between ACT adherence and ORS, and the change questionnaire (i.e. the SPQ; Pearson/Spearman correlation)
4. Early change in stable problems	Therapy coincides with changes in long-standing client problems	Change in outcome measures from baseline to initial sessions (Pearson/Spearman correlation, visual analysis)
5. Event-shift sequences	Important events precede stable shifts in client problems, especially if therapy process and client change are logically related	Correspondence between within therapy measure (HAT) and variation in patient's problem (SPQ; Pearson/Spearman correlation, visual analysis)

Note: HAT – Helpful Aspects of Therapy form. SPQ – Simplified Personal Questionnaire.

Table 2

Evidence for links between nontherapy processes and outcome, from Elliott (2002)

Nonchange/ nontherapy area	Changes are...	Method of evaluation (analysis method)
1. Non-improvement	Either trivial or negative.	Assess reliable and clinical significance on measures (RCI calculations); ask ppt the importance and direction of any change (Change Interview).

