Data from throughout the study will be cross-referenced to develop the affirmative and sceptic briefs required for the HSCED. Pseudonyms will be used for the participants and there will be no patient identifiable information within the briefs. Once completed, the briefs will be sent to the expert panel of three Clinical Psychologist, with relevant interest and experience of psychotherapeutic change methods. The panel adjudicate over the case material using a semi-structured questionnaire to decide whether the client made a substantial change and where they attribute this towards (ACT-specific, non-specific, or extra-therapeutic factors). This process allows for a reduction in researcher bias.

SCHEDULE OF PROCEDURES

Procedures	Visits									
	Psychology Screening Assessment & Baseline 1 (wk1)	Baseline 2 (wk2)	Baseline 3 (wk3)	Baseline 4 & Session 1 - pre (wk4)	Sessions 2-5 (wks 5-8)	Session 6 - mid (wk 9)	Sessions 7-11 (wks 10-14)	Session 12 - post (wk 15)	Change Interview (wk 16)	Six wk follow-up (wk 20)
Informed consent	x									
Symptom, & process measures	x	x	x	x		x		x		x
Demographics	x									
Medical history	x						x			
ACT intervention				x	x	x	x	x		
Session, change, & fidelity measures				x	x	x	x	x		
Change Interview									x	

Note: wk = week; see Timetable of Measures for outline of when individual measures are administered.

WITHDRAWAL

Participants may be withdrawn from the trial either at their own request or at the discretion of the Investigator. The participants will be made aware that this will not affect their future care. Participants will be made aware (via the information sheet and consent form) that should they withdraw the data collected to date may not be erased in accordance with the University's Research Privacy Notice and information given in the Participant Information Sheet and may still be used in the final analysis.

Stopping rules and discontinuation:

- If a participant withdraws consent to continue.
- If a participant expresses that the intervention is causing their anxiety and depression to get worse.
- If a participant's physical health significantly deteriorates to a point where continuation would be impractical or create sufficient negative burden on them.
- If a participant fails to comply with the intervention.
- If new findings become published regarding likely risks or negative effects of ACT.

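### The panel must separate ACT-specific from non-specific change, but no planned analysis sets ACT adherence against the therapeutic alliance, so change driven by alliance could be credited to ACT

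*Combined protocol and SAP*

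**What the plan says.** The question is three-way. The third question under SECONDARY OBJECTIVE(S) is "What specific factors (ACT-specific, non-specific, extra-therapeutic) contribute to observed changes". At the end of STUDY REGIMEN the expert panel decides whether the client changed and "where they attribute this towards (ACT-specific, non-specific, or extra-therapeutic factors". STUDY BACKGROUND and RATIONALE describes "non-specific factors common to all psychotherapies (e.g. the therapeutic alliance or a client's expectations of treatment". It says of the design, with modality-specific, non-specific and extra-therapeutic factors in view, that "it actively seeks to measure and analyse these".

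The briefs are framed differently. Under STUDY DESIGN, "The purpose of the affirmative brief is to demonstrate direct links between the therapeutic intervention and outcomes", while "The opposing sceptic brief demonstrates possible nontherapy processes which could account for change".

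DATA ANALYSIS gives the evidence areas: five in Table 1 for the affirmative brief and eight in Table 2 for the sceptic brief. Table 1 row 2 uses "Correlations between within therapy measures (HAT), and quantitative outcome measures". Row 3 uses "Correlations between ACT adherence and ORS, and the change questionnaire". The TABLE OF OUTCOMES has SRS, the alliance measure, collected at every session. CompACT-8, the measure of psychological flexibility, is collected at the baselines, mid-therapy, post-therapy and follow-up.

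**The concern.** A client can improve in therapy because of what is particular to ACT or because of a good working relationship. Both count as therapy, so a contrast of therapy with non-therapy does not separate them. Most Table 1 areas (the client credits therapy, early change, shifts after notable sessions) could be met by a treatment that worked through the relationship alone.

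Row 3 comes closest to ACT-specific evidence. However, a session that goes well may score high on adherence and on alliance, and row 3 as written does not look at the second. If the sceptic brief is not asked to argue the alliance explanation either, the panel may reach an ACT-specific verdict without that rival having been put to it. Question 3, the study's question about mechanism, is what is at stake.

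**Working it through.** The plan has no figure of its own on this point. Its one sample-size calculation, 3 / (1 − 0.25) = 4, reproduces but has no bearing here. The check is mainly textual.

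**Step 1: which rows address a non-specific factor?**

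| Row | Content | Tests alliance as a cause of real change? |
|---|---|---|
| Table 1, rows 1 and 4 | Client attribution; early change | No |
| Table 1, rows 2 and 5 | HAT against outcomes or SPQ | Not required; HAT content might bear on it |
| Table 1, row 3 | ACT adherence against ORS and SPQ | No; SRS absent |
| Table 2, row 3 | Wish to please therapist or researcher | No; concerns superficial change |
| Table 2, row 4 | Client expectations | No; a different non-specific factor |
| Table 2, row 8 | Effects of being in research | No; concerns the researcher |
| Table 2, rows 1, 2, 5, 6, 7 | Non-improvement, artefact, self-correction, life events, psychobiology | No |

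SRS is named in 0 of 5 + 8 = 13 rows, and CompACT-8 in 0 of 13. One of the 13 rows (expectations) explicitly covers a factor that the protocol calls non-specific. None requires the alliance argument.

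**Step 2: what could row 3 show if only alliance mattered?** Every input here is an assumption except the number of sessions (up to 12, Therapeutic sessions).

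- Model: alliance A is standard normal in each session. Adherence = aA + √(1 − a²)·e₁ and ORS = aA + √(1 − a²)·e₂, with independent errors and no direct effect of adherence on ORS.
- Expected correlation of adherence with ORS = a × a = a².
- Two-sided 5% critical value at n = 12 (10 df): |r| > 0.576. The plan sets no threshold, so this is only a yardstick.
- 20,000 simulated clients for each value of a:

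| a | a² | Significant positive r | Significant positive partial r given SRS |
|---|---|---|---|
| 0.4 | 0.16 | 7% | 2.5% |
| 0.6 | 0.36 | 21% | 2.3% |
| 0.8 | 0.64 | 66% | 2.4% |

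The nominal one-direction rate is 2.5%. The last column treats SRS as an error-free measure of alliance and sessions as independent. With real data the adjustment would be less complete.

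**Step 3: how much can the data in hand support?** With 12 points the Fisher-z standard error is 1/√(12 − 3) = 0.33. For an observed r of 0.36, z = 0.377, the 95% limits are 0.377 ± 1.96 × 0.333 = −0.276 to 1.030, and back-transformed they are −0.27 to 0.77. A partial correlation would need |r| > 0.60. Ranking SRS against adherence is therefore mostly noise within one client, and the comparison has to be descriptive.

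CompACT-8 has 4 baselines + mid + post + follow-up = 7 occasions, of which 3 fall on session days (sessions 1, 6 and 12). It cannot support a week-to-week correlation. It can support a reliable-change calculation or a visual comparison of timing.

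**The case against.** The strongest reply is that absence of a name from the tables does not mean exclusion. OPQOL-brief, the primary outcome, and HADS are also named in none of the 13 rows, and nobody would conclude that they go unused. Several rows speak generically of measures or outcome measures. The rich case record holds the quantitative and qualitative data, and STUDY REGIMEN says data from the whole study are cross-referenced to build both briefs.

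Exclusion criterion 3 itself gives alliance as an example of a non-therapeutic process, so a sceptic author could treat it as within scope. Table 2 row 4 covers expectations. The Change Interview, held by someone the client has not met before, asks what change is attributed to, and the panel has non-specific among its answers.

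All of this stands, and it defeats two stronger readings that a reader might infer. One is that SRS and CompACT-8 never enter the evidence; the documents leave them a route in. The other is that alliance-driven change would necessarily be credited to ACT. The panel can decide otherwise, the plan sets no threshold for row 3, and two Table 1 areas are needed even to warrant adjudication.

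The reply does not supply a planned comparison. A route into the case record is not an instruction to weigh alliance against ACT. The row that uses adherence names its variables, and SRS is not among them. Calling alliance non-therapeutic makes the lack of an alliance row in the nontherapy table more noticeable.

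**Conclusion.** The concern holds as a gap in how the evidence is organised. The attribution asked of the panel is three-way. The planned evidence areas do little to separate ACT-specific from alliance effects, because row 3 of Table 1 omits SRS and no row of Table 2 requires the alliance argument. Alliance-driven change could therefore be credited to ACT.

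The textual finding rests on no assumption. Its practical size cannot be derived from the documents. The 7% to 66% range depends on assumed equal loadings of 0.4 to 0.8, independent sessions and a significance yardstick that the plan does not use. It shows that the error is possible, and how strongly its frequency depends on the size of the alliance effect; it does not predict the result. The efficacy question, whether clients improve on OPQOL-brief, is not affected.

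**What to change.** 1. Add a row to Table 2 for non-specific therapy factors (alliance). The sceptic brief would argue that change came through the relationship, drawing on SRS by session, HAT entries and Change Interview content.
2. In Table 1 row 3, present the SRS–ORS and SRS–SPQ relations beside those for ACT adherence, as plots and descriptive correlations without a pass/fail rule. State that at most 12 points are available. State also that the client completes SRS and ORS together, so shared reporting may inflate their agreement; SPQ is completed before the session and is less exposed to this.
3. Have any ACT-specific claim report CompACT-8 change, by RCI or visual sequencing, next to OPQOL-brief change, and say so when the two disagree. Note that a gain on CompACT-8 alone does not exclude alliance as its cause. The reference list gives its validation as a manuscript in preparation, so the source of the reliability figure for the RCI should be stated.

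The cost is wording in two tables and a few more plots per client, with no new data, visits or staff. The downside is a little more analysis, and fewer cases may be classed as ACT-specific.

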3. Client's (qualitative) views on individual therapy sessions assessed with the Helpful Aspects of Therapy form (HAT; Lewlyn, Elliott, Shapiro, Firth, & Hardy, 1988). Completed by therapist in discussion with participant.

Fidelity measure

1. Adherence to ACT related processes assessed with the ACT Fidelity Measure (ACT-FM; O'Neill, Latchford, McCracken & Graham, 2019). Completed by therapist and secondary researcher.

EXPLORATORY OUTCOMES

Adaptations made to treatment will be recorded so that commentary can be made on what adaptations to ACT may be beneficial for older adult clients. **Consideration of the impact that delivering the intervention in a remote manner will also be made and any adaptations that were made to facilitate this.**

TABLE OF OUTCOMES

Objectives	Outcome Measures	Timepoint(s) of evaluation of this outcome measure (if applicable)
Primary Objectives	1. Quality of life (OPQOL-brief).	1. Baselines, pre-, mid- and post-intervention, and at six-week follow up.
Secondary Objectives	Symptom measures 1. Cognitive functioning (MoCA). 2. Changes in levels of anxiety and depression (HADS).	1. At initial contact, by service as standard practice. 2. At initial contact, by service as standard practice. Baselines, pre-, mid- and post-intervention,

		and at six-week follow up.
	Change measures 
 1. Client's goals (PQ). 2. Client's view on change (Change Interview). 	
 1. Prior to each weekly treatment session. 2. One week after finishing treatment.
	Process measure 
 1. Psychological flexibility (CompACT-8). 	
 1. Baselines, pre-, mid- and post-intervention, and at six-week follow up.
	Session measures 
 1. Quality of life/general outcomes (ORS). 2. Therapeutic alliance (SRS). 3. Client's views on the therapy session (HAT). 	
 1-3. At the end of each weekly treatment session.
	Fidelity measures 
 1. Fidelity of treatment (ACT-FM). 	
 1. At the end of each session (by therapist) and random sampling of all sessions (by Secondary Research Supervisor).

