Up to 12 therapeutic sessions will be offered, delivered by the student researcher/therapist. At session 1 (week 4), confidentiality will be reiterated, including under what circumstances confidentiality would be broken (risk to them or others). They will also be explained the procedure of clinical supervision from [name] as well as ACT-supervision from [name] (the latter supervision not using confidential information). Participants will then be supported to complete the Simplified Personal Questionnaire (SPQ), noting their expectations for therapy, the main problems they are bothered with and duration of these. Participants will then be introduced to the underlying concepts of ACT, before starting with the proposed ACT-protocol (adapted from Petkus & Wetherell, 2013):

ACT area	Sessions and content
Values	Sessions 1-3 1. Regaining contact with values: What matters? 2. The role of religion 3. Making the most of the remaining time
Acceptance/Willingness	Sessions 4-5

	
 1. What's worked? What hasn't? What are the costs? 2. Control is the problem 3. Experiencing vs. avoiding 4. How does this fit with values?
Defusion	
Sessions 6-7
 
 1. Awareness of internal experiences 2. A thought is just a thought 3. Having a thought vs. content of a thought 4. Defusion from damaged conceptualized self
Mindfulness and Self as Context	
Sessions 8-9 (Mindfulness exercise conducted at the beginning of every session)
 
 1. Being in the present moment 2. Not judging thoughts or feelings 3. Thoughts and selves
Committed Action	
Begins during the Values sessions and continues throughout the intervention, but is emphasized during Sessions 10-12
 
 1. What goals are consistent with values? 2. What actions work toward these goals? 3. Breaking it down into steps 4. Problem-solving potential barriers 5. Enlisting support
Therapeutic blueprint	
Session 12
 
 1. Summary of the content 2. Review of SPQ and any change experienced 3. Next steps and further support options

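### Table 1 row 3 aims at week-to-week change but correlates score levels over at most 12 sessions, so a shared time trend can look like a process-outcome link

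*Combined protocol and SAP*

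**What the plan says.** All references are to the Combined protocol and SAP.

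- **Target.** DATA ANALYSIS, Table 1 row 3, describes the evidence sought as "In-therapy process variables covary with week-to-week changes in client problems".
- **Method.** The method column of that row gives "Correlations between ACT adherence and ORS, and the change questionnaire" (the SPQ), by Pearson or Spearman. Row 2 states how the coefficient is chosen: "Pearson correlation, or Spearman correlation if assumptions of normal distribution not met". No alpha, and no size of r that counts as evidence, is given.
- **Number of points.** STUDY REGIMEN, Therapeutic sessions: "Up to 12 therapeutic sessions will be offered, delivered by the student researcher/therapist".
- **Timing (TABLE OF OUTCOMES).** ACT-FM is scored "At the end of each session (by therapist) and random sampling of all sessions (by Secondary Research Supervisor". The PQ is completed "Prior to each weekly treatment session" and the ORS "At the end of each weekly treatment session".
- **Weight.** STUDY DESIGN, Affirmative brief: there are five areas of direct evidence, and a case needs at least two of them to go to adjudication.

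No section mentions differencing, detrending, lags, a session covariate or serial correlation. Rows 4 and 5 of Table 1 add visual analysis; row 3 does not.

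**The concern.** The adherence, ORS and SPQ values are ordered in time within one person. They are not independent pairs. If therapy goes as hoped, ORS rises and the problem ratings improve over the sessions. If adherence also moves in one direction, the two sets of levels correlate because both follow session number, whether or not a high-adherence week is followed by a better week. Serial dependence within each series adds to this. The Pearson-or-Spearman choice rests on normality, which has nothing to do with a common trend.

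Nothing in Table 2 covers the gap. Row 2 (statistical artefacts) deals with measurement error, outlying values and multiple testing. Row 5 (self-correction) looks only from baseline to the initial sessions. Neither addresses two series moving together during therapy.

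Row 3 is the only row of Table 1 that uses the adherence measure. It therefore bears directly on the third guiding question under SECONDARY OBJECTIVE(S), which separates ACT-specific from non-specific and extra-therapeutic factors.

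**Working it through.** **The plan's own figures.** None is given for this correlation. The only sizing figure is the sample: three cases with about 25% dropout gives 3 / (1 - 0.25) = 4, which matches the planned maximum. The present point does not depend on it.

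**Inputs from the documents.** At most 12 sessions per client; adherence, ORS and SPQ recorded at every session; plain Pearson or Spearman.

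**Assumed inputs, because the documents give none.** Two-sided 5% criterion. Each series rises linearly by D residual SD from first to last session, with D from 0 to 3. Lag-1 autocorrelation is 0 to 0.5. There is no true link between the series.

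**Critical value.** r = t / sqrt(df + t²). With n = 12, df = 10 and t = 2.228: 2.228 / sqrt(10 + 4.964) = 0.576.

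**Expected size of the spurious r.** A linear rise of D over 12 equally spaced sessions has sample variance 0.107 D². With unit residual variance, r is roughly 0.107 D² / (1 + 0.107 D²).
- D = 2: 0.43 / 1.43 = 0.30.
- D = 3: 0.97 / 1.97 = 0.49. The simulated mean is 0.50.

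**Simulated share of unlinked clients with a significant positive Pearson r (nominal 2.5%).** The range is for autocorrelation 0 to 0.5.

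| Shared rise | Pearson on levels | Pearson given session number |
|---|---|---|
| 1 SD | 5-9% | 2.5-4.1% |
| 1.5 SD | 8-15% | 2.5-4.1% |
| 2 SD | 15-25% | 2.5-4.1% |
| 3 SD | 39-51% | 2.5-4.1% |

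Spearman on levels gives 14-22% at 2 SD and 36-46% at 3 SD. If lower SPQ scores mean improvement, the sign reverses and the size does not.

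**If adherence is flat.** The two-sided rate is 5% without autocorrelation, whatever the client's trend. With autocorrelation 0.5 it is about 10-15% for client trends of 1 to 3 SD.

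**Adherence level against week-to-week change.** The two-sided rate is 1.8-5.1% across the settings. The session-adjusted correlation gives 5.0-8.4% two-sided, so slight inflation remains under autocorrelation.

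**Precision of the alternatives.** Twelve ratings give 11 changes. For an observed r of 0.5, Fisher's z is 0.549 with standard error 1 / sqrt(11 - 3) = 0.354. The interval on the z scale is 0.549 ± 1.96 × 0.354, or -0.144 to 1.242, which is r from -0.14 to 0.85. The partial correlation with n = 12 and one covariate has the same standard error, 1 / sqrt(12 - 1 - 3).

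**The case against.** Five points can be made for the plan.

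1. **Drift in adherence is not documented.** A reader might infer it from the ordering of the ACT components. The documents do not support that: the session protocol is described as a guide to be adapted to the individual, mindfulness opens every session, and Committed Action "Begins during the Values sessions and continues throughout the intervention, but is emphasized during Sessions 10-12". That ordering concerns content, not an adherence score. This stands. Drift is a plausible premise given a trainee therapist under weekly ACT supervision (STUDY SETTING), and no more.

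2. **The row's description already points to change scores.** Read that way, the problem largely disappears. But the method column names the measures with no change score, so description and method need to be reconciled.

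3. **The consequence is limited.** A reader might infer that two areas of evidence establish the affirmative case. They only admit the case to adjudication. A sceptic brief, rebuttals and a panel of three Clinical Psychologists follow, and the primary outcome (OPQOL-brief) is not in this row. This stands. The panel might raise the trend itself, but that is not a planned control.

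4. **An error rate is only a proxy.** The analysis is descriptive and feeds a narrative brief, with no stated threshold. True, but a correlation of 0.3 to 0.5 produced by time alone would mislead a descriptive reader as well.

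5. **The alternatives are weak with so few points.** With a true within-session correlation of 0.5, the session-adjusted test would be significant in 36% of clients with 12 sessions and 21% with 8. This stands, and is why an interval should be reported and significance should not be the rule.

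**Conclusion.** The point holds in a limited form. Row 3's stated method does not test its stated target, and nothing elsewhere in the plan handles a shared time trend.

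The size depends on assumptions the documents cannot settle: 12 sessions, a two-sided 5% criterion, linear trends and autocorrelation of 0 to 0.5. Spurious positive results run from about 5-9% at a 1 SD shared rise to 39-51% at 3 SD. With flat adherence and no autocorrelation there is no inflation.

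A reader might conclude that an improving client will necessarily produce false evidence for ACT. The documents and the figures do not support that: false evidence becomes more likely if adherence trends, but is not certain. Nor do they support extending the point to Table 1 row 5, where the HAT is listed as a qualitative measure and visual analysis is already planned.

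The effect is to weaken one of five lines of affirmative evidence. The change is worth making because it costs almost nothing.

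**What to change.** In Table 1 row 3, adopt one of two analyses and name it before the data are examined:

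- correlate session adherence with the week-to-week change in SPQ and in ORS. State which SPQ rating is paired with which session: the SPQ is completed before the session and adherence is scored at its end, so same-session pairing puts the problem rating before the process meant to explain it; or
- use the partial (or partial rank) correlation of adherence with ORS and SPQ, controlling for session number.

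The first is closer to the row's own description. With either, report n, a 95% interval and a plot of both series by session. Keep the plain correlation of levels as description only.

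**Cost.** One derived variable or one covariate, a plot, and a sentence or two in Table 1. With 12 or fewer points the estimate will be imprecise, and genuine benefit that appears only as parallel linear improvement will be credited less.
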